10.1.4 Measurement Time Points

The outcome will be measured as long as the patient remains without progression and getting scans for assessment. Patients will be followed for survival as long as they remain consented.

10.1.5 Response Review

Response will be independently reviewed by a radiologist, though primary assessment will remain with the treating physician.

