10. MEASUREMENTS

Primary Outcome Measure

Definition: Overall response defined as either complete response or partial response assessed using RECIST v1.1 criteria. This measure will be reported as a number without dispersion.

- Title: overall response
- Time Frame: 8 (+/-4) weeks from start of treatment.
- Safety Issue: No

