12. STATISTICAL CONSIDERATIONS

12.1 Statistical Design

This is an open-label, single cohort study designed to evaluate the activity of targeted therapy in anaplastic/undifferentiated thyroid cancer. There will be no randomization. An optimal Simon 2 stage design will be utilized to address the primary objective.

Anaplastic or Undifferentiated thyroid cancer patients without curative option will be considered eligible for this trial. Due to the rarity of the disease and difficulty in establishing the diagnosis

of anaplastic thyroid cancer, cases of anaplastic thyroid cancer can be classified as undifferentiated thyroid cancer. For this purpose, both undifferentiated and anaplastic thyroid cancer cases will be eligible.

There is no effective treatment for anaplastic thyroid cancer in the locally recurrent or metastatic setting for untreated *BRAF V600E* negative or *BRAF V600E* positive ATC/UTC AFTER dabrafenib and trametinib. Abemaciclib will be administered to the patient until disease progression by RECIST, unacceptable toxicity, withdrawal of consent, or discontinuation of the trial for any other reason. Patients who have RECIST-defined PD as assessed by the investigator but who, in the opinion of the investigator, have evidence of continued clinical benefit from abemaciclib may continue to receive the study medication. In such cases, these patients must continue to be followed for safety and efficacy assessments as per the schedule of assessments.

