12.2 Interim analyses

We plan to conduct one interim analysis for futility. Following an optimal Simon 2 stage design, we will enroll 9 patients and assess overall response. If 0 patients have overall response, we will stop the study for futility. Otherwise, we will continue the study and enroll 8 more patients. At the end of the study, if 3 or more patients have overall response, we will deem this treatment strategy acceptable.

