12.4.2. Analysis Plan

Our primary analysis will be the calculation of the overall response rate, defined as the percentage of patients who have overall response in the full analysis set. The rate of overall response and its 95% confidence interval in the full analysis set will be estimated using exact binomial method.

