12.6.2 Sample size justification

The sample size calculation is based on Simon's two-stage design (Simon, 1989). Simon's optimal two-stage design will be used for conducting the trial. The null hypothesis is that the true response rate is 0.05 (5%), and the alternative hypothesis is that the true response rate is 0.3 (30%). The trial is carried out in two stages.

In stage I, a total number of 9 patients is accrued. If there are 0 response among these 9 patients, the study will be early stopped.

Otherwise, additional 8 patients will be accrued in stage II, resulting in a total number sample size of 17. If there are 3 or more responses among these 17 patients, we reject the null hypothesis and claim that the treatment is promising. The design controls the type I error rate at 0.05 and yields the power of 0.9.

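### The treating physician's read decides both Simon rules and the primary response rate, while the planned independent radiologist review has no stated analytic use and the type I error has little margin for over-called responses

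*Combined protocol and SAP*

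**What the plan says.** Section 12.1: "This is an open-label, single cohort study", with no randomization. Section 10 gives the primary endpoint: "Overall response defined as either complete response or partial response assessed using RECIST v1.1 criteria".

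Section 10.1.5 names two readers. "Response will be independently reviewed by a radiologist", "though primary assessment will remain with the treating physician".

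Three later sections use the response count:
- Section 12.2, after 9 patients: "If 0 patients have overall response, we will stop the study for futility". Otherwise 8 more are enrolled, and 3 or more responses in 17 make the treatment acceptable.
- Section 12.4.2 defines the primary response rate, "defined as the percentage of patients who have overall response in the full analysis set", with an exact binomial 95% confidence interval.
- Section 12.6.2 sets the null rate at 5% and the alternative at 30%, and states: "The design controls the type I error rate at 0.05 and yields the power of 0.9".

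None of these three sections names a reader. The documents contain no rule for disagreement between the two reads, no analysis based on the radiologist's read, and no statement of whether the radiologist is masked to the treating physician's assessment.

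**The concern.** Section 10.1.5 gives the primary assessment to the treating physician and nothing in section 12 changes that. The natural reading is that this person's call settles whether stage 2 opens, whether the drug is declared promising, and what response rate is reported. There is no control arm to offset optimistic reading. A second, independent read is planned, but no decision or estimate uses it.

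The thresholds are low, so single calls matter. One response in 9 opens stage 2 for 8 further patients, and three in 17 lead to a larger study (section 12.7). A partial response turns on a 30% fall in summed diameters. Section 10.1.3 asks for two observations at least 4 weeks apart for a complete response but not for a partial one, and the best-response table lists no confirmation requirement for a partial response. One scan judged close to the 30% line could therefore tip either rule.

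**Working it through.** **Inputs from section 12.6.2:** n1 = 9, stop at 0 responses; n2 = 8, total 17; promising if total ≥ 3; p0 = 0.05; p1 = 0.30; stated type I error 0.05 and power 0.9.

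**Step 1. Reproduce the design.** With X1 ~ Bin(9, p) and X2 ~ Bin(8, p),

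P(promising) = P(X1=1)·P(X2≥2) + P(X1=2)·P(X2≥1) + P(X1≥3).

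- At p = 0.05: 0.2985 × 0.0572 + 0.0629 × 0.3366 + 0.0084 = 0.0171 + 0.0212 + 0.0084 = 0.0466 (from unrounded terms).
- At p = 0.30: 0.1557 × 0.7447 + 0.2668 × 0.9424 + 0.5372 = 0.9045.
- Early stopping under the null: 0.95^9 = 0.630, so stage 2 opens with probability 0.370.

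A grid search for the optimal design with type I error ≤ 0.05 and power ≥ 0.90 returns the same design. The plan's figures are right for error-free reads. The margin to 0.05 is 0.05 − 0.0466 = 0.0034.

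**Step 2. Allow over-calls.** Let f be the probability that a true non-responder is called a responder. The observed null rate is 0.05 + 0.95f. The values of f are assumed; the documents give none.

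| f (assumed) | Observed null rate | Type I error | Early stopping under null |
|---|---|---|---|
| 0 | 0.0500 | 0.0466 | 0.630 |
| 1% | 0.0595 | 0.071 | 0.576 |
| 2% | 0.0690 | 0.101 | 0.525 |
| 5% | 0.0975 | 0.212 | 0.397 |
| 10% | 0.1450 | 0.433 | 0.244 |

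The error passes 0.05 when the observed null rate passes 0.0514, that is f = (0.0514 − 0.05)/0.95 ≈ 0.15%. At f = 5%, the expected number of false responses if all 17 are read is 17 × 0.95 × 0.05 = 0.81.

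**Step 3. Fewer patients who can be misread.** Section 2.1.1 gives a median survival of 3–4 months. If only half of the true non-responders could be misread (assumed), the observed null rate is 0.05 + 0.95 × f/2. For f = 2% this is 0.0595 and the error 7.1%; for f = 5% it is 0.07375 and the error 11.7%.

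**Step 4. The price of changing the reader.** Suppose the independent read makes no false calls but confirms only a fraction c of true responses (assumed). The observed rate under the alternative is 0.30c.

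| c (assumed) | Observed rate | Power | Stopping at 0 of 9 |
|---|---|---|---|
| 100% | 0.300 | 0.905 | 0.040 |
| 95% | 0.285 | 0.882 | 0.049 |
| 90% | 0.270 | 0.855 | 0.059 |
| 80% | 0.240 | 0.787 | 0.085 |

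**The case against.** Investigator assessment is an openly declared choice, nothing in the documents contradicts it, and it is a legitimate option in a 17-patient activity screen whose success leads only to a confirmatory study. That stands: this is a design improvement, not an internal error.

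A reader might infer that the stated type I error is wrong. It is not. Section 12.6.2 is correct as calculated, and inflation arises only if over-calls occur, at a rate the documents do not give. Nor do they give a source for the 5% null or say on which reader's scale it lies. If it is an investigator-read rate, some over-calling is already in it and the inflation shrinks or disappears. Patients who progress or die before a scan stay in the full analysis set but can hardly be read as partial responders, which also reduces the effect (step 3).

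It is also tempting to call the radiologist's read unbiased and already paid for. Section 10.1.5 says only that it is independent; masking, timing and funding are not stated, and in a one-arm trial the radiologist may know the treatment too.

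Some safeguards exist. Target lesions are fixed at baseline, the same technique is used throughout and imaging is preferred (10.1.2, 10.1.3). The monitoring committee's audit may cover source documents (11.1), and the investigators' calls review subject data (11.5). These narrow discretion but do not give the independent read any role.

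Finally, an independent reader can miss true responses. In a population described as having no effective treatment, wrongly stopping for futility matters. Step 4 shows that this cost is real.

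**Conclusion.** The point holds as a recommended change. The deciding read lies with the treating physician in an open-label one-arm trial, and the planned independent read has no stated analytic use. That the physician's call feeds all three uses is a reading of section 10.1.5 together with section 12's silence on the reader.

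The size is conditional. The error is 0.0466 with error-free reads, and 7.1%, 10.1% or 21.2% if 1%, 2% or 5% of all true non-responders are over-called. Those rates are assumed, apply to every true non-responder, and treat the 5% null as a true response rate. The calculation shows a thin margin; it does not show that the error exceeds 5% in this trial. Moving to the independent read restores 0.0466 only as far as that read is itself free of over-calls.

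**What to change.** In sections 10.1.5, 12.2 and 12.4.2, pre-specify that the planned independent RECIST read, made without access to the treating physician's assessment, is the read counted for the stage 1 rule, the final rule and the primary response rate. Report the treating physician's response rate and the agreement between the two reads beside it.

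At the least, pre-specify as a sensitivity analysis the response rate with its exact confidence interval, and the 3-of-17 outcome, by the independent read.

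Do not require both readers to agree: a true response missed by either one would then be lost.

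Sample size and thresholds stay as they are, and no additional reader is needed. The costs are a short wait for the read at the stage 1 look, and some power if the independent read misses true responses (0.905 to 0.882 at 95% confirmation, 0.855 at 90%; assumed rates). Treatment decisions are unaffected.

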10.2 Secondary Outcome Measures

- 1) Overall survival defined as duration of time from start of treatment to death from any cause. This will be reported as median survival time with interquartile range.
- 2) Progression-free survival (PFS) defined as the duration of time from start of treatment to time of progression or death from any cause. This will be reported as median time with interquartile range.
- 3) Safety analysis of AEs.

11. MULTISITE REGULATORY CONSIDERATIONS

11.1 Monitoring plan

The Stanford Cancer Institute Data and Safety Monitoring Committee (DSMC) will be the monitoring entity for this study. The DSMC will audit study-related activities approximately once per year to determine whether the study has been conducted in accordance with the protocol, local standard operating procedures, FDA regulations, and Good Clinical Practice (GCP). This may include review of the following types of documents participating in the study: regulatory binders, case report forms, eligibility checklists, and source documents. In addition, the DSMC will regularly review serious adverse events and protocol deviations from all sites associated with the research to ensure the protection of human subjects. Results of the DSMC audit will be communicated to the IRB and the appropriate regulatory authorities at the time of continuing review, or in an expedited fashion, as needed.

11.2 Protocol Review and Amendments

The protocol, the proposed informed consent and all forms of participant information related to the study (e.g. advertisements used to recruit participants) will be reviewed and approved by the Stanford IRB and Stanford Cancer Institute Scientific Review Committee (SRC). Any changes made to the protocol will be submitted as a modification and will be approved by the IRB prior to implementation. The Protocol Director and/or study team will disseminate the protocol amendment to all participating investigators. Investigators will be expected to obtain IRB approval within 90 days for all amendments.

11.3 Data management

The Protocol Director, or his/her designee, will prepare and maintain adequate and accurate participant case histories with observations and data pertinent to the study. Study specific Case Report Forms (CRFs) will document treatment outcomes for data analysis. Case report forms will be developed using the REDcap database system and will be maintained by the clinical trial coordinators. CRFs will be kept in a locked office, only accessible to the research team.

Registration and deviations will be recorded on OnCore. Refer to sections 3.4 and 7.4 for additional details on reporting and data management.

11.4 Study Documentation

The Protocol Director and participating site investigators must maintain adequate and accurate participant case histories with observations and other data pertinent to the study. Original source documents should be transcribed to Case Report Forms (CRFs) and used to communicate study data to the lead site. Source documents include hospital records, clinical charts, laboratory and pharmacy records, and recorded electronic data.

Participating Center's PIs will be responsible for maintaining the clinical protocol and subjects' study charts, reporting adverse events, assuring that consent is obtained and documented, and reporting the status of the trial in continuing renewals submitted to their IRB and trial monitoring group(s) as per their facility protocol.

11.5 Site Communication

When all participating institutions have successfully received IRB approval *and* have started enrolling patients, teleconferences to discuss participants and study-related matters will be held at a mutually agreed time, although calls may occur more frequently if needed.

Teleconferences will be coordinated by Research staff at a participating institution; PIs, Research Coordinators, Nurses, and Co-Investigators if needed will participate. Any issues with patient compliance, database entry, or other items will also be discussed in these calls. Calls will include review by PIs of subject data to assure validity as well as the safety of subjects; and the progress of the trial may also be discussed. At times of study renewal or more frequently if needed, PIs will review safety reports and clinical trial efficacy endpoints and confirm that the safety outcomes favor continuation of the study.

12. STATISTICAL CONSIDERATIONS

12.1 Statistical Design

This is an open-label, single cohort study designed to evaluate the activity of targeted therapy in anaplastic/undifferentiated thyroid cancer. There will be no randomization. An optimal Simon 2 stage design will be utilized to address the primary objective.

Anaplastic or Undifferentiated thyroid cancer patients without curative option will be considered eligible for this trial. Due to the rarity of the disease and difficulty in establishing the diagnosis

of anaplastic thyroid cancer, cases of anaplastic thyroid cancer can be classified as undifferentiated thyroid cancer. For this purpose, both undifferentiated and anaplastic thyroid cancer cases will be eligible.

There is no effective treatment for anaplastic thyroid cancer in the locally recurrent or metastatic setting for untreated *BRAF V600E* negative or *BRAF V600E* positive ATC/UTC AFTER dabrafenib and trametinib. Abemaciclib will be administered to the patient until disease progression by RECIST, unacceptable toxicity, withdrawal of consent, or discontinuation of the trial for any other reason. Patients who have RECIST-defined PD as assessed by the investigator but who, in the opinion of the investigator, have evidence of continued clinical benefit from abemaciclib may continue to receive the study medication. In such cases, these patients must continue to be followed for safety and efficacy assessments as per the schedule of assessments.

12.1.1 Randomization

There is no randomization.

12.2 Interim analyses

We plan to conduct one interim analysis for futility. Following an optimal Simon 2 stage design, we will enroll 9 patients and assess overall response. If 0 patients have overall response, we will stop the study for futility. Otherwise, we will continue the study and enroll 8 more patients. At the end of the study, if 3 or more patients have overall response, we will deem this treatment strategy acceptable.

12.3 Descriptive Statistics and Exploratory Data Analysis

Demographic, disease characteristics and other baseline data will be summarized descriptively for the full analysis set. Treatment compliance and duration of treatment exposure will also be summarized for both the full analysis and safety set. Categorical data will be presented as frequencies and percentages. For continuous data, mean, standard deviation, median, 25th and 75th percentiles will be presented.

12.4 Primary Analysis

12.4.1 Analysis Population

The Full Analysis Set (FAS) comprises all consented patients who receive at least one dose of abemaciclib.

The Safety Set includes all patients who received at least one dose of abemaciclib medication.

12.4.2. Analysis Plan

Our primary analysis will be the calculation of the overall response rate, defined as the percentage of patients who have overall response in the full analysis set. The rate of overall response and its 95% confidence interval in the full analysis set will be estimated using exact binomial method.

12.5 Secondary Analysis

12.5.1 Analysis Population

The analysis population will include all consented patients who receive at least one dose of abemaciclib.

12.5.2 Analysis Plan

Overall survival (OS) is defined as the time from start of treatment to death due to any cause. If a subject is not known to have died, then OS will be censored at the latest date the subject was known to be alive. The OS distribution will be estimated using the Kaplan-Meier method, and the Kaplan-Meier curves, medians and 95% confidence intervals of the medians will be presented.

Progression-free survival is defined as the time from start of treatment to date of progression or death due to any cause. If a subject is not known to have progressed or died, then PFS will be censored at the latest date the subject was known to be alive or disease-free. The PFS distribution will be estimated using the Kaplan-Meier method, and the Kaplan-Meier curves, medians and 95% confidence intervals of the medians will be presented.

In addition, we will estimate response duration using Kaplan-Meier methods.

For all safety analyses, the safety set will be used. Toxicities will be dichotomized as none versus any adverse event, or none and mild versus moderate to severe adverse event.

Summary tables for adverse events (AEs) will include only AEs that started or worsened during the on-treatment period, the treatment-emergent AEs, unless otherwise specified.

All safety data collected in the study will be listed regardless of the study period with data collected during the pre-treatment and post-treatment period flagged. The incidence of treatment-emergent adverse events (new or worsening from baseline) will be summarized by system organ class and or preferred term, severity (based on CTCAE grades), type of adverse event, relation to study treatment by the Principal Investigator and/or research team.

Deaths reportable as SAEs and non-fatal serious adverse events will be listed by patient and tabulated by type of adverse event.

Specific safety event categories (SEC) will be considered. Such categories consist of one or more well-defined safety events which are similar in nature and for which there is a specific clinical interest in connection with the study treatment(s).

For each specified category, number and percentage of patients with at least one event per category will be summarized.

Handling of missing values/censoring/discontinuations

All attempts will be made to ensure that the database contains complete information. No imputation will be applied for missing data.

12.6 Sample Size

12.6.1 Accrual estimates

As a rare cancer, ATC patients are seen at <10/year at SCI. However, because treatment options are so uncommon it is expected the patients in the region will be attracted to come to SCI specifically to participate in this study.

12.6.2 Sample size justification

The sample size calculation is based on Simon's two-stage design (Simon, 1989). Simon's optimal two-stage design will be used for conducting the trial. The null hypothesis is that the true response rate is 0.05 (5%), and the alternative hypothesis is that the true response rate is 0.3 (30%). The trial is carried out in two stages.

In stage I, a total number of 9 patients is accrued. If there are 0 response among these 9 patients, the study will be early stopped.

Otherwise, additional 8 patients will be accrued in stage II, resulting in a total number sample size of 17. If there are 3 or more responses among these 17 patients, we reject the null hypothesis and claim that the treatment is promising. The design controls the type I error rate at 0.05 and yields the power of 0.9.

12.6.3 Effect size justification

There are limited data describing the efficacy of drugs targeting CDK4/6 in ATC. This protocol is designed to determine their efficacy in a patient population for whom there are limited data currently.

12.7 Criteria for future studies

If the overall response rate criteria is met, then a larger study in more patients will be undertaken to confirm the overall response rate and any potential benefit in improving survival outcomes.

Ethical considerations and administrative procedures

Regulatory and ethical compliance

This clinical study was designed, shall be implemented and reported in accordance with the ICH Harmonized Tripartite Guidelines for Good Clinical Practice, with applicable local regulations (including European Directive 2001/20/EC and US Code of Federal Regulations Title 21), and with the ethical principles laid down in the Declaration of Helsinki.

Informed consent procedures

Eligible patients will only be included on this after providing written (witnessed, where required by law or regulation), IRB/IEC/REB-approved informed consent.

Informed consent must be obtained before conducting any protocol-specific procedures (i.e. all of the procedures described in the protocol). The process of obtaining informed consent should be documented in the patient source documents. The date when a subject's Informed Consent was actually obtained will be captured in the clinical trial record. The informed consent document will be approved by the IRB.

Discontinuation of the study

This study will discontinue if terminated by the Institutional Review Board or at the discretion of the Principal Investigator.

Publication of the study and results

The results of this study will be updated and posted per regulatory requirements, including (but not limited) to databases such as clinicaltrials.gov.

(b) Communication and Publication of Clinical Trial Results

All submitted manuscripts will comply with institutional guidelines and with authorship guidelines of the International Committee of Medical Journal Editors.

Study documentation, record keeping and retention of documents

The investigator/institution should maintain the trial documents as specified in Essential Documents for the Conduct of a Clinical Trial (ICH E6 Section 8) and as required by applicable regulations and/or guidelines. The investigator/institution should take measures to prevent accidental or premature destruction of these documents.

Confidentiality of study documents and patient records

